10.6.1 Summary Statistics

Shift tables summarising the number (%) of subjects that shifted between all combinations of baseline and end-of-treatment values for the overall interpretation will be produced. The number of subjects with that baseline values will be used as denominator when percentages are calculated (e.g. the percentage of subjects going from normal to not clinically significant abnormal will be using the number of subjects being normal at baseline as denominator).

The number of subjects with ovarian cyst will be summarised at baseline and at end-of-treatment.

The endometrial thickness at baseline, at end-of-treatment and the change from baseline to end-of-treatment will be summaries by time point.

10.6.2 Data listings

All subjects with any abnormalities at any visit and/or any ovarian cyst at any visit will be listed with all TVU evaluations.

11 Interim Analyses

No interim analysis is planned for this trial.

12 Deviations from Protocol Analysis

The Study Protocol stated that the primary analysis should be adjusted for site. In this SAP the primary analysis is not adjusted for site, this change has been made because of the actual distribution of subjects on sites. We have 4 out of 6 sites with 4 or less subjects. Adjustment for site leads to a high risk of noninformative sites.

The study was planned to be have a randomisation ratio of 2:1 with 2 subjects receiving quinagolide for each subject receiving placebo, however it was discovered, after LPLV and before database lock, that the randomisation list used during the study had a 1:1 ratio between quinagolide placebo. The use of a 1:1 ratio instead of a 2:1 ratio will increase the power to detect a difference between quinagolide vaginal ring and placebo vaginal ring.

The use of the 1:1 randomization ratio, have not led to any change of the planned analysis in this SAP.

13 References

- [2] Rubin, D. B. (1987). *Multiple Imputation for Nonresponse in Surveys*. New York, John Wiley and sons.

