4.2.2 Randomisation

At the RM+7 visit (visit 2) of cycle -1, eligible subjects will be randomised in a 2:1 ratio to quinagolide vaginal ring dose load 1080 µg or placebo vaginal ring, administered once per menstrual cycle and sequentially for four menstrual cycles (cycles 1, 2, 3 and 4).

An independent statistician will create a computer-generated randomisation list and randomisation is performed centrally through the Interactive Response Technology (IRT) system prior to the insertion of the first vaginal ring. Thereby each subject will receive a unique randomisation number generated in the IRT system. Randomisation is stratified by site.

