9.6.2 Primary Endpoint

For each type of lesion (endometrioma, DIE and adenomyosis), the primary endpoint is the change in the sum of the lesion sizes at cycle 4, i.e. the difference between the active treatment group and the placebo group in the change from baseline in the sum of the lesion sizes of the same type at the end of cycle 4. The baseline is defined as the sum of the sizes of all lesions of the same type ≥ 10 mm obtained from the MRI examination at screening. At end-of-treatment / cycle 4, the sizes of all lesions included at baseline of the same type will be summed. For each type of lesions, subjects with at least one lesion of that type ≥ 10 mm at baseline will be included.

For each type of lesions, the primary endpoint will be analysed using an analysis of covariance (ANCOVA) model, with the change in the sum of lesion sizes from baseline measured at cycle 4 as the dependent variable, the baseline sum of lesions as covariate, the treatment group and site as fixed effect. The treatment difference between active treatment versus placebo will be reported with 95% confidence interval and corresponding p-value for each of the three types of lesions:

$$\begin{cases} H_0^{P1} : \mu_{QVR}^1 = \mu_{Placebo}^1 \\ H_1^{P1} : \mu_{QVR}^1 \neq \mu_{Placebo}^1 \end{cases}$$

$$\begin{cases} H_0^{P2} : \mu_{QVR}^2 = \mu_{Placebo}^2 \\ H_1^{P2} : \mu_{QVR}^2 \neq \mu_{Placebo}^2 \end{cases}$$

$$\begin{cases} H_0^{P3} : \mu_{QVR}^3 = \mu_{Placebo}^3 \\ H_1^{P3} : \mu_{QVR}^3 \neq \mu_{Placebo}^3 \end{cases}$$

Where (H_0^{P1}) , (H_0^{P2}) , (H_0^{P3}) are the null hypotheses for each of the 3 types of lesions, (H_1^{P1}) , (H_1^{P2}) , (H_1^{P3}) are the alternative hypotheses for each of the 3 types of lesions, and

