3.2 Data presentation

Due to the trial design including separate analysis of the primary endpoint for each of the three types of lesion (endometrioma, DIE and adenomyosis), some presentations will be performed by type of lesion, some will be performed for the three types of lesions combined, and some will be performed both by type and combined. Additionally, some presentations are also prepared by type of disease (i.e. endometriosis and adenomyosis), where the category of endometriosis combines endometrioma and DIE.

A subject will be included in the by type analysis if she has at least one lesion of that type ≥ 10 mm at baseline. Notice that a subject can be included in the analysis of more than one type of lesions.

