9.1 General Considerations

All efficacy endpoints will be summarised using descriptive statistics and will be performed by treatment and in total for each of the three types of lesion (endometrioma, DIE and adenomyosis), for endometriosis (endometrioma and DIE), and for the three types of lesions combined.

Categorical data will be summarised using numbers and percentages (n and % of all observed) in addition to the sum ‘All’, the percentages are based on the total number of subjects with a corresponding assessment in the analysis set. Continuous data will be presented, using the number of subjects (n), mean and standard deviation, median, 25th percentile, 75th percentile, minimum, and maximum, unless otherwise specified.

All statistical tests will be performed using a two-sided test at a 5% significance level. Treatment differences will (where appropriate) be presented with 95% confidence intervals and p-values corresponding to the statistical test of the hypothesis of “equal effect” against the alternative of “different effect”.

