9.2.1 Primary Analyses

The primary analyses are based on the FAS.

For each type of lesion (endometrioma, DIE and adenomyosis), the primary endpoint is the change in the sum of the lesion sizes at end-of-treatment, i.e. the difference between the active treatment

group and the placebo group in the change from baseline in the sum of the lesion sizes of the same type at the end-of-treatment. The baseline is defined as the sum of the sizes of all lesions of the same type ≥ 10 mm obtained from the MRI examination at screening. At end-of-treatment / cycle 4, the sizes of all lesions included at baseline of the same type will be summed. For each type of lesions, subjects with at least one lesion of that type ≥ 10 mm at baseline will be included.

If a subject is prematurely discontinued during or after cycle 2, an end-of-treatment MRI examination will be performed. The results from this end-of-treatment MRI will be used to calculate the primary endpoints.

If the end-of-treatment MRI examination results in an assessment of a lesion size as <5 mm without a precise value (or categorised as detectable), the size of this lesion will be imputed as 2.5 mm. If the end-of-treatment MRI examination results in a lesion assessed as being truly not detectable, the size of this lesion will be imputed as 0 mm.

If the end-of-treatment MRI examination is not performed or is missing, the missing measurement will be imputed using a multiple imputation (MI) strategy. The imputation will be based on a missing at random assumption (MAR). The missing sum of lesion sizes at end-of-treatment will be imputed by regression-based imputation models using treatment group, baseline sum of lesion sizes, and the overall NRS score (at visit 2, 5, 6, 7, 8) as the predictors. The imputation procedure will be repeated 100 times. For technical reasons, the imputation is implemented in two steps as described below.

Firstly any non-monotone missingness of the predictors mentioned above is imputed using the Markov chain Monte Carlo (MCMC) method, assumptions underlying this partial imputation step are such that subjects with missing data follow the same model as other subjects with the same value of the observed predictors that have complete data, and this is a reasonable assumption for this partial imputation, because subjects tend to miss intermediate visits due to scheduling conflicts or other reasons unrelated to their medical condition under study.

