9.2.2 Sensitivity Analyses

A number of sensitivity analyses are planned to establish robustness of the primary analysis, including summary statistics (expect for the placebo based MI in section 9.2.2.2). All sensitivity analysis except the PP analysis will be performed on the FAS.

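### Does dropping site from the primary model call for a site-adjusted sensitivity analysis?

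*SAP*

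**What the plan says.** Protocol section 4.2.2 says: "Randomisation is stratified by site". It names no other stratum. Protocol section 9.6.2 gives the primary ANCOVA the baseline sum of lesion sizes as covariate, with "the treatment group and site as fixed effect".

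The SAP's primary ANCOVA (section 9.2.1) has baseline and treatment only. Section 12 declares this: "In this SAP the primary analysis is not adjusted for site". It gives the reason: "We have 4 out of 6 sites with 4 or less subjects", which creates a risk of sites that carry no information on the treatment contrast.

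The imputation model in SAP 9.2.1 works by "using treatment group, baseline sum of lesion sizes, and the overall NRS score (at visit 2, 5, 6, 7, 8) as the predictors", so it has no site term either. SAP 9.2.2 opens with: "A number of sensitivity analyses are planned to establish robustness of the primary analysis". The analyses listed under it are per protocol, two without imputation, placebo-based imputation, actual treatment, small lesions included, and adjustment for previous hormonal treatment. None includes site. On efficacy summaries, SAP 9.1 says: "All efficacy endpoints will be summarised using descriptive statistics and will be performed by treatment and in total". They are split by lesion type but not by site.

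Site does appear elsewhere in the SAP:
- Disposition, treatment completion and MRI attendance, by treatment and lesion type, are repeated by site (4.2 to 4.4).
- Baseline summaries for the combined set, including number and size of lesions, are given by treatment within site (section 7 and 7.1.4).
- All observed endpoints are listed by site and treatment (9.6).

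**The concern.** A stratification factor normally belongs in the analysis model, and here the protocol put it there. The SAP took it out once the site distribution was known, and no supportive analysis shows what the protocol's model would have given. The stated reason counts against a six-level factor. It does not in itself rule out pooling the small sites, and the SAP does not discuss pooling.

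The lesion sets make the question sharper. SAP 3.2 says: "Notice that a subject can be included in the analysis of more than one type of lesions". Lesion type is not a named stratum. Stratifying all randomised subjects by site therefore does not guarantee that the arms are balanced by site within each of the three analysed sets. If site predicts change in lesion size, chance imbalance could move the unadjusted estimate in a set of about 24 subjects.

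**Working it through.** **1. The plan's own figure.** Inputs from Protocol 9.1 and SAP 3.3: difference 6 mm, SD 4.5 mm, 16 and 8 subjects, two-sided 5% t-test.

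- SE = 4.5 × √(1/16 + 1/8) = 1.949 mm.
- Noncentrality = 6/1.949 = 3.079, with 22 df and critical t = 2.074.
- Noncentral-t power = 83.7%, against the stated 83%.

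The SAP reports that allocation was in fact 1:1. With 12 and 12, SE = 1.837 mm, noncentrality = 3.266 and power = 87.7%.

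**2. Degrees of freedom at n = 24.** Residual df = 24 − 2 − (number of covariate terms).

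| Model | Residual df | Power, 12/12, from df alone |
|---|---|---|
| SAP: baseline and treatment | 24 − 2 − 1 = 21 | 87.6% |
| Plus site pooled to three levels | 24 − 2 − 3 = 19 | 87.2% |
| Plus six sites | 24 − 2 − 6 = 16 | 86.5% |

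The df loss is small. The larger cost comes from imbalance between treatment and site, which needs simulation.

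**3. Simulation.** The documents give no site variance, block size or site counts by lesion type. Assumed here: blocks of 4 within site, 1:1 allocation, total SD 4.5 mm, site share of variance 0%, 10% or 30%, and three splits of 24 subjects (9/8/2/2/2/1, 6/6/4/3/3/2 and 10/10/1/1/1/1), with 4,000 trials per setting. Each entry is the range over the three splits.

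| Site share | Type I error, no site | Power, no site | Power, pooled | Power, six sites |
|---|---|---|---|---|
| 0% | 4.7–5.1% | 85.6–86.0% | 83.2–84.2% | 76.9–81.0% |
| 10% | 4.2–4.5% | 86.8–87.5% | 86.7% | 81.0–85.8% |
| 30% | 3.6–4.2% | 88.7–90.4% | 91.4–93.1% | 89.8–93.1% |

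Mean 95% CI width is 7.78–7.81 mm without site and 7.94–8.06 mm pooled at a 0% share. At 30% it is 7.36–7.61 mm and 6.90–7.20 mm. Leaving site out does not inflate type I error. Whether pooling helps depends on a variance that nobody knows in advance.

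**4. What a pooled-site analysis would show.** From SAP section 12, the four small sites hold at most 4 × 4 = 16 subjects. Assume 72 randomised, sites of 34/24/4/4/3/3, blocks of 4, and a lesion set that is a random subset of the 72.

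- The pooled level is empty or has one arm only in about 10% of sets of 24, 23% of sets of 18 and 47% of sets of 12.
- With 24 subjects and a true 6 mm effect, the adjusted and unadjusted verdicts at p < 0.05 differ in 6.4% of trials with no site effect and 7.7% at a 30% share. Repeat runs gave 6.0–6.8% and 6.8–7.7%. Most of this disagreement comes from adding two terms to a small model and not from site.
- The two estimates differ by more than 1 mm in 7% of trials with no site effect and 16% at a 30% share.
- With 12 subjects, the verdicts differ in about 16% of trials when site has no effect, and pooling widens the CI by 5% to 16% for site shares from 30% down to 0%.

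**The case for a change.** The best case for acting is that the cost is one paragraph and one extra model per lesion type, and that the change departs from the protocol's primary model, which is what robustness analyses are meant to probe. The protocol also treats site as a source of MRI variability: section 3.5.1 restricts centres and machine brands, and relies on cross-calibration and central reading to limit it. Those measures reduce site differences without proving that there are none. Pooling by blinded counts would avoid the worst of the sparse-site problem.

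Part of this stands. The facts are right, and a statistician could run such a model without harm if it stayed outside the Hochberg decision and site were dropped wherever the pooled level is empty or one-armed. Three things weaken the case:

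- Site counts carry no treatment or outcome information, so a choice based on them is not driven by results.
- The departure is narrower than it looks. It concerns the primary model and those defined as similar to it. For imputation, Protocol 9.6.1 names baseline MRI results and unspecified other measurements. The repeated-measures models in Protocol 9.6.3 list no site term.
- The by-site disposition tables, together with the endpoint listings by site and treatment, already let a reader check treatment-by-site balance within each lesion set.

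**Conclusion.** No change follows; this is a fair and declared trade-off. The SAP's reason for dropping a six-level site factor is borne out: with no site effect, that factor would cost roughly 5 to 9 points of power at n = 24. The unadjusted analysis remains valid, with simulated type I error of 3.6% to 5.1%, and chance site imbalance under randomisation is not bias. A pooled factor would move power by about 2 to 3 points in either direction, depending on a site variance the documents do not give. In the smaller lesion sets it would often meet the same sparse-site problem that the SAP sought to avoid. An analyst who follows the SAP as written gets sound results, and the extra model is at most an optional supportive analysis.

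These sizes rest on assumptions not in the documents: block size 4, the site splits shown, site share of variance from 0% to 30% and, for the pooling figures, 72 randomised and lesion sets drawn at random. The type I error result held for all three splits tried. The empty-or-one-arm figures depend more on the assumed site sizes.

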Appendix 1 Markedly Abnormal Laboratory Safety Values, Vital Signs and ECGs

Table 1: Markedly abnormal Criteria for Laboratory Tests

Variable	Units	Markedly abnormal Criteria	
		Low	High
Haematology			
Haemoglobin	g/L	≤ 80	Not applicable
Haematocrit	Ratio	>0.20	>0.60
Total WBC	10 ⁹ /L	<2.0	>35.0
Platelets	10 ⁹ /L	<50	>999
Total RBC	10 ¹² /L		Not applicable
Clinical Chemistry			
AST	IU/L	Not applicable	> 155
ALT	IU/L	Not applicable	> 165
Alkaline phosphatase	IU/L	Not applicable	> 520
GGT	IU/L	Not applicable	> 180
Total bilirubin	µmol/L	Not applicable	≥ 1.5xULN
Creatinine	µmol/L	Not applicable	>252
Albumin	g/L	<20	
Sodium	mmol/L	≤ 130	≥ 155
Potassium	mmol/L	≤ 3.0	>6.0
Phosphorus	mmol/L	>0.65	
Calcium	mmol/L	<1.75	>3.13
Glucose	mmol/L		>13.9
Total cholesterol	mmol/L	Not applicable	>10.36

Table 2: Markedly abnormal Criteria for Vital Signs*

Variable	Criterion Value	Change from Baseline
Systolic blood pressure	≥ 180 mmHg ≤ 90 mmHg A drop of 20 mmHg from changing position	Increase of ≥ 20 mmHg Decrease of ≥ 20 mmHg
Diastolic blood pressure	≥ 105 mmHg ≤ 50 mmHg A drop of 10 mmHg from changing position	Increase of ≥ 15 mmHg Decrease of ≥ 15 mmHg
Pulse rate	≥ 120 bpm ≤ 50 bpm	Increase of ≥ 15 bpm Decrease of ≥ 15 bpm
Body weight	None	Increase of ≥ 7% Decrease of ≥ 7%
Body temperature	≥ 38.3° C	Increase to ≥ 39.4° C

* To be identified as markedly abnormal, a treatment value must meet the criterion value and also the specified change from baseline.

Table 3: Abnormal Criteria for Quantitative ECG Data

Variable	Baseline	Abnormal Treatment-Emergent Value
ECG heart rate	Normal	≤ 50 bpm and decrease from baseline of ≥ 15 bpm ≥ 120 bpm and increase from baseline of ≥ 15 bpm
Duration of PR interval	Normal	≥ 220 msec
Duration of QRS interval	Normal	≥ 120 msec
Duration of QTc interval	Normal	≥ 450 msec
Duration of QTc interval	Normal	≥ 480 msec
Duration of QTc interval	Normal	≥ 500 msec
Duration of QTc interval*	Not applicable	Increase from baseline of ≥ 30 msec
Duration of QTc interval	Not applicable	Increase from baseline of ≥ 60 msec

* QTc will be calculated both using Bazett's and Fridericia's correction formulae.

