3.1.2 Trial Flow Chart

Table 3-1 Trial Flow Chart – Procedures at Clinic Visits

	Screening ^{a,b}			Treatment Period ^b						Follow-up
	Wash-out ^a	Cycle -1 start	Cycle -1 end	Cycle 1			Cycle 2	Cycle 3	Cycle 4	
		Screening visit (V1)	Randomisation (V2)	V3	V4	V5	V6	V7	V8	Phone call
	~1-3 months before V1	RM+7	RM+7	1-5 days of V2	7-14 days of V2	RM+7	RM+7	RM+7	RM+7 / EOT	~1 month after V8
Written informed consent	X ^a	X ^a								
Inclusion/exclusion criteria	X ^a	X	X ^c							
Demographics		X								
Medical/menstrual/repro history		X								
Body measurements		X								
Vital signs		X	X ^c	X					X	
Physical examination		X							X	
Gynaecological examination		X							X	
Cervical cytology ^d		X								
Transvaginal ultrasound (TVU) ^f		X							X	
Urine pregnancy test ^g		X	X ^c			X ^h	X ^h	X ^h	X ^h	
Randomisation			X							
Blood sample (safety)		X				X ⁱ			X	
Blood samples (endocrine)			X ^h	X			X ^h		X ^h	
Blood samples (biomarkers)			X ^h						X ^h	
Blood sample (PK)				X	X	X ^h	X ^h	X ^h	X ^h	
MRI		X ^e							X ^e	
B&B scale			X ^h						X ^h	
NRS			X ^h			X ^h	X ^h	X ^h	X ^h	
EHP-30 questionnaire			X ^h				X ^h		X ^h	
Vaginal ring dispensing			X			X	X	X		
Insertion (i) / removal (r) of ring			i			i,r	i,r	i,r	r	
Drug accountability						X	X	X	X	
Menstrual bleeding pattern			X			X	X	X	X	
Concomitant medications	X	X	X	X	X	X	X	X	X	X
Adverse events	X	X	X	X	X	X	X	X	X	X
Condom dispensing / reminder		X	X	X	X	X	X	X		
End-of-treatment form									X	

B&B=Biberoglu and Behrman Scale, EHP-30=Endometriosis Health Profile 30 Questionnaire, EOT=end-of-treatment, i=insertion, NRS=Numerical Rating Scale, PK=pharmacokinetic(s), r=removal, RM+7=day 7 after return of menses, V=visit.

a Subjects who are currently using some hormonal contraceptives (including combined oral contraceptive pill, transdermal patch and contraceptive ring) may be eligible for the trial if they have completed the wash-out period (if applicable) and have return of menses. In this case, subjects need to sign the informed consent before the wash-out. Subjects not requiring wash-out will sign the informed consent at the screening visit.

b A menstrual cycle in this trial is considered the period between RM+7 in a cycle until the following RM+7 in the next cycle. The RM+7 visit can be scheduled 6-10 days after return of menses (RM+6-10) and is always at the end of each cycle. An exception is cycle -1 which starts with RM+7 of a prior cycle.

c Performed before randomisation.

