10.3 Safety Laboratory Variables

Safety lab values are planned to be measured twice, at baseline (visit 1), at end-of-treatment (visit 8). If multiple blood samples are obtained prior to first dose of IMP the last blood sampling performed prior to the first dose of IMP is used as baseline.

Laboratory variables will be grouped under “Haematology” and “Clinical Chemistry”.

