10.3.3 Markedly Abnormal Changes

For each laboratory variable, a summary tables will be prepared displaying the number and percentage of subjects in each treatment group with normal baseline values but having at least one pre-specified markedly abnormal value any time after first dose of IMP. Pre-specified markedly abnormal criteria for laboratory tests are given in Appendix 1.

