10.3.4 Data Listings

All laboratory values will be listed by subject number and time point. Values outside the reference range (with information on clinically significance) and markedly abnormal values will be flagged.

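### SAP Appendix 1 prints the Low limits for haematocrit and phosphorus with the sign reversed, so ordinary values count as markedly low and truly low ones do not

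*SAP*

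**What the plan says.** Protocol 9.8 leaves the criteria for markedly abnormal laboratory values to the SAP, and SAP 10.3.3 takes them from Appendix 1. Table 1 there has a Low and a High column. The two rows at issue are "Haematocrit Ratio >0.20 >0.60" and "Phosphorus mmol/L >0.65"; the phosphorus limit stands in the Low column and its High cell is blank. Rows close by show the usual pattern, with either a strict or a non-strict sign: "Calcium mmol/L <1.75 >3.13" and "Sodium mmol/L ≤ 130 ≥ 155".

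The limits are used in two places:

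- SAP 10.3.3 counts subjects with "normal baseline values but having at least one pre-specified markedly abnormal value any time after first dose of IMP".
- SAP 10.3.4 says of the listings: "Values outside the reference range (with information on clinically significance) and markedly abnormal values will be flagged".

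Both analytes are in the planned panel (protocol 7.2.8). The share of subjects with markedly abnormal changes is part of a secondary endpoint (SAP 2.2.2). SAP 10.3 plans one safety sample at baseline and one at end of treatment. The SAP flow chart (Table 3-1) adds a visit 5 sample at Italian sites only.

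**The concern.** A Low criterion should pick out values at or beneath a lower limit. SAP 10.3.2 uses the word in that sense for the shift tables. With a greater-than sign, the two rows select the opposite set: everything above a limit that is meant to mark an extreme low.

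A program written literally from the appendix would label almost every subject markedly low for these analytes and leave the truly low subjects unmarked. A programmer who silently corrected the sign would depart from criteria that the SAP calls pre-specified, with no record of it. No other section of either document gives different limits, so nothing in the plan settles the conflict.

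**Working it through.** The plan states no figure to reproduce here; the check is of the table's logic.

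**1. Signs by column (SAP Appendix 1, Table 1).**

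| Column | Numeric limits | Sign agrees with column | Sign conflicts |
|---|---|---|---|
| Low | 9 | 7: < for WBC, platelets, albumin, calcium; ≤ for haemoglobin, sodium, potassium | 2: haematocrit, phosphorus |
| High | 14 | 14 (all > or ≥) | 0 |
| Total | 23 | 21 | 2 |

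**2. Overlap within rows.** Six analytes have both limits: haematocrit, WBC, platelets, sodium, potassium and calcium. In five of them no value can meet both rules. For haematocrit, every value above 0.60 is also above 0.20, so the Low rule contains the High rule.

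**3. The printed rule applied to single values.**

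| Value | Low as printed | Low with sign reversed | High |
|---|---|---|---|
| Haematocrit 0.15 | no | yes | no |
| Haematocrit 0.40 | yes | no | no |
| Haematocrit 0.61 | yes | no | yes |
| Phosphorus 0.50 mmol/L | no | yes | no limit |
| Phosphorus 1.20 mmol/L | yes | no | no limit |

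**4. Effect on the reported share, with no assumed distribution.** For a subject with one post-dose value X and limit L, P(X > L) = 1 − P(X ≤ L). If p is the true share at or below the limit, the printed Low rule reports 1 − p:

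- p = 0% is reported as 100%
- p = 5% is reported as 95%
- p = 10% is reported as 90%

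For two arms, (1 − pA) − (1 − pP) = −(pA − pP), so the difference changes sign. As an illustration, a true 5% against 0% prints as 95% against 100%.

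These identities need a single post-dose sample. At Italian sites a subject is counted if either of two values exceeds L. That can only raise the flagged share, and it means exact reversal of the difference is not guaranteed there.

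**5. Effect under assumed distributions.** The central laboratory supplies the reference ranges and they are not in the documents, so the means and SDs below are assumptions. With a normal model, the flagged share is Φ((mean − L)/SD).

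| Analyte | Assumed mean, SD | (mean − L)/SD | Flagged Low as printed |
|---|---|---|---|
| Haematocrit, L = 0.20 | 0.36, 0.05 | 0.16/0.05 = 3.20 | 99.93% |
| Haematocrit, L = 0.20 | 0.42, 0.03 | 0.22/0.03 = 7.33 | 100.00% |
| Phosphorus, L = 0.65 | 1.0, 0.20 | 0.35/0.20 = 1.75 | 95.99% |
| Phosphorus, L = 0.65 | 1.2, 0.15 | 0.55/0.15 = 3.67 | 99.99% |
| Phosphorus, wider case | 0.9, 0.25 | 0.25/0.25 = 1.00 | 84.1% |

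In every row the shortfall from 100% is the share at or below the limit, which is the group that should have been marked. The model is not conditioned on a normal baseline, as the SAP 10.3.3 count is. No subject count is given, because the number analysed is not stated.

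**The case against.** The strongest reply is that this is a clerical slip with little reach. It touches two analytes in one descriptive table and one listing flag, with no test attached. Low values still appear in the SAP 10.3.2 shift tables, the out-of-range flags in 10.3.4 and the investigator's laboratory review (protocol 7.2.8). Haemoglobin, in the row above haematocrit, has a correctly signed Low limit of ≤ 80 g/L. A table showing nearly everyone as markedly low would probably be noticed at output review. All of this stands, and it limits the seriousness without making the printed rule usable.

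Three narrower points also stand:

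- The output would be inverted rather than empty: with one sample, p can be recovered as one minus the printed share.
- The evidence is weaker for phosphorus. It has no High limit, so the case rests on the convention of the column and not on a contradiction within the row. That nearly every subject would be flagged rests on an assumed distribution.
- The documents cannot confirm that 0.20 and 0.65 are themselves the intended numbers.

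An error in reading the PDF cannot be excluded. It is unlikely, because < and ≤ are intact in the other seven Low cells, including the rows directly above and below both faulty ones. If the phosphorus limit were a High limit in the wrong column, the row would still be wrong and would flag the same values.

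**Conclusion.** The concern holds. Two of the nine Low limits point the wrong way, and nothing elsewhere in the protocol or SAP corrects them. As written, the SAP 10.3.3 table and the markedly-abnormal flag mark ordinary haematocrit and phosphorus values as markedly low and pass over truly low ones. Only the 10.3.3 count is restricted to subjects with a normal baseline; the 10.3.4 flag covers every listed value, so its reach is wider.

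The sign conflict rests on no assumption. The percentages do: the 1 − p result needs a single post-dose sample, and the flagged shares need the distributions assumed above. The primary analysis and the efficacy endpoints are not affected. This should be fixed because it feeds a listed safety endpoint, but it does not threaten the trial's main conclusion.

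**What to change.** Before database lock:

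1. Reverse the sign in the Low cells for haematocrit (0.20) and phosphorus (0.65), after checking both cells against the sponsor's source criteria.
2. State for each whether the limit is < or ≤, since the column uses both (four rows <, three rows ≤).
3. Check the derivation program behind the 10.3.3 table and the listing flags against the corrected appendix.

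If the database is already locked, record the correction in the clinical trial report. The cost is two sign edits and the matching program lines, with no new data.
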